15.1.3. Sensitivity Analysis of Primary Efficacy Variable(s)

The primary analysis will be repeated for the PPS.

•

Document: T:\PROJ\Medinol\CXA27472\06_Biostatistics\Documentation\SAP\Final

1.0_08Aug2018\JNIR01_SAP_Final V1.0_08Aug2018.docx

Author: [name] Version Number: Final V1.0 Version Date: 08Aug2018

Template No: CS_TP_BS016 Revision 4 Reference: CS_WI_BS005

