4.3. Changes to Analysis from Protocol

The protocol uses the term clinically driven and ischemia driven interchangeably. This SAP defines
revascularization events accordingly to the term "clinically driven" as this is consistent with the CEC
adjudication form.

Document: T:\PROJ\Medinol\CXA27472\06 Biostatistics\Documentation\SAP\Final

1.0_08Aug2018\JNIR01_SAP_Final V1.0_08Aug2018.docx

Author: [name] Version Number: Final V1.0 Version Date: 08Aug2018

Template No: CS TP BS016 Revision 4 Reference: CS WI BS005

Effective Date: 01Apr2016

Copyright © 2009, 2010, 2012, 2016 Quintiles Transnational Corp. All rights reserved.

- The protocol defines the as-treated (AS) population which contains only those Japanese patients who
 received the study stent. However, this population is not used in any of the analyses and will not be
 defined in this SAP.
- The protocol suggests a sensitivity analysis based on modified definitions of peri-procedural myocardial infarction (universal definition and modified SCAI definition). This analysis will not be performed for the purpose of assessing the non-inferiority of JNIR01 to BIONICS in terms of Target Lesion Failure at 12 months.

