6.2. FULL ANALYSIS SET [FAS]

The Full Analysis Set (FAS) will contain all enrolled Japanese patients regardless of whether they were given MedJ-01.

Document: T:\PROJ\Medinol\CXA27472\06 Biostatistics\Documentation\SAP\Final

1.0_08Aug2018\JNIR01_SAP_Final V1.0_08Aug2018.docx

Author: [name] Version Number: Final V1.0 Version Date: 08Aug2018

Template No: CS TP BS016 Revision 4 Reference: CS WI BS005

Effective Date: 01Apr2016

Copyright © 2009, 2010, 2012, 2016 Quintiles Transnational Corp. All rights reserved.

Patients are considered enrolled after the guidewire has successfully been passed beyond the target lesion. If the study stent could not be implanted due to reasons that are not related to study device, the patient will be de-registered and will not be considered part of the FAS. Patients not receiving the study stent after it has been advanced beyond the guiding catheter will be analyzed in the FAS. Patients enrolled in the trial with major deviations will also be analyzed in the FAS.

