6.3. PER PROTOCOL SET [PPS]

The Per Protocol Set (PPS) will contain all patients who receive the study stent with no major protocol violations. Major protocol violations include enrollment of a patient:

- · whose informed consent was not properly obtained
- who did not meet all of the inclusion or exclusion criteria
- who did not receive the study stent due to any reason
- who did not receive at least 12 months of Dual Antiplatelet Therapy (DAPT) post baseline procedure. Details of DAPT to be received post-procedure are given in Section 6.4.9.3 of the protocol.

Major protocol violations leading to exclusion from the PPS will be summarized using the FAS.

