1.0_08Aug2018\JNIR01_SAP_Final V1.0_08Aug2018.docx

Author: [name] Version Number: Final V1.0 Version Date: 08Aug2018

Template No: CS TP BS016 Revision 4 Reference: CS WI BS005

Effective Date: 01Apr2016

Copyright © 2009, 2010, 2012, 2016 Quintiles Transnational Corp. All rights reserved.

are known to confound the relationship between study-stent and outcome:

Covariates considered in propensity-score matching:

Clinical Parameters (as captured in the eCRF):

- Age
- Gender
- Prior MI
- · Medically treated diabetes Mellitus
- Prior Revascularization (Either previous PCI or previous CABG captured on the medical history eCRF form)
- Acute Coronary Syndrome

Pre-procedure Angiographic Parameters (as reported in the Quantitative Coronary Angiography (QCA) data):

- · Diameter Stenosis
- Reference Vessel Diameter
- Calcification
- TIMI Flow (Pre-procedure)
- Tortuosity
- SYNTAX Score
- Lesion located at LAD

After each patient in both JNIR and BIONICS has received a propensity score, these two groups will be combined and partitioned into propensity score quintiles.

Finally, each JNIR patient in quintile x is matched with 4 random BIONICS patients from the same quintile x. If no remaining BIONICS patients are left to match with JNIR patients in one of the five quintiles, the next closest quintile will be used to choose a BIONICS patient.

The clinical and angiographic covariates used in the propensity-score matching will be summarized for the FAS by treatment group.

The proportion of TLF as well as proportions of cardiac death, target vessel related MI and clinically-driven TLR at 12 months along with the corresponding exact 95% CIs will be presented for the JNIR group and matched BIONICS group. The difference in proportion will be reported. Farrington-Manning one-sided p-value and upper bound of the one-sided 90% CI of the difference in proportion between JNIR and matched BIONICS groups will be presented.

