17. SAFETY OUTCOMES

All outputs for safety outcomes will be based on the Safety Analysis Set unless otherwise specified.

Only data of the JNIR trial will be presented for the safety outcomes. In particular, there will be no statistical comparisons between JNIR and BIONICS trials for the safety outcomes.

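### The per-protocol repeat of the primary comparison defines its filter for JNIR only and gives no BIONICS counterpart, so the plan's sole sensitivity analysis is not like-for-like as written

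*SAP*

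**What the plan says.** SAP 15.1.3 contains one sentence: "The primary analysis will be repeated for the PPS". Nothing else tests the robustness of the primary result. SAP 4.3 withdraws the analyses under alternative definitions of periprocedural MI, saying "This analysis will not be performed for the purpose of assessing the non-inferiority of JNIR01 to BIONICS". SAP 8.3 does not impute missing outcomes, and SAP 8.6 plans no subgroup analyses.

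The analysis sets are written for JNIR. SAP 6.2: "The Full Analysis Set (FAS) will contain all enrolled Japanese patients regardless of whether they were given MedJ-01". SAP 6.3: "The Per Protocol Set (PPS) will contain all patients who receive the study stent with no major protocol violations". The violations listed there are improper consent, failed eligibility, no study stent, and a patient "who did not receive at least 12 months of Dual Antiplatelet Therapy (DAPT) post baseline procedure". The last item points to the JNIR protocol: "Details of DAPT to be received post-procedure are given in Section 6.4.9.3 of the protocol". Membership of the sets is agreed before the database lock of this trial (SAP 6).

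The primary analysis in SAP 15.1.2 has two sides: JNIR, and BIONICS patients drawn 4:1 within propensity-score quintiles. DAPT agent and persistence are not among the matching covariates. Concomitant medications (SAP 17.6.1) fall under SAP 17, where "Only data of the JNIR trial will be presented for the safety outcomes".

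**The concern.** A repeat of the primary analysis needs a BIONICS side, and the SAP does not say what that side is once the PPS replaces the FAS. It does not say whether BIONICS patients must meet any per-protocol criterion, whether the propensity score is re-estimated, or whether matches are redrawn.

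The DAPT criterion is the difficult one because it spans the same 12 months as the endpoint. Under the literal wording, a JNIR patient who has a cardiac death in month 5 cannot have had 12 months of DAPT. That patient leaves the PPS and takes a TLF event along. If BIONICS is not filtered, a matched patient with the same history stays in and counts as a failure. Matching on baseline covariates cannot repair a selection that happens after baseline.

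What is at stake is the value of the check. The comparison is non-randomised, and this is the only analysis that could show whether the FAS result is fragile. If one side is selected and the other is not, neither agreement nor disagreement between FAS and PPS can be interpreted.

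**Working it through.** The plan gives no figure for the PPS analysis, so there is none to reproduce. The check is an illustration with the plan's own design inputs.

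**Inputs from the documents**
- Margin 0.05; one-sided level 0.10 (SAP 8.5 and 15.1.2).
- 100 JNIR patients, 5% loss, 4:1 matching, TLF rate 0.058 (protocol 7.5). This gives 95 evaluable JNIR patients and 4 × 95 = 380 matched BIONICS patients, with 0.058 × 380 = 22 events.

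**Assumptions (no figure in the documents)**
- 7 TLF events among the 95 JNIR patients in the FAS.
- 10 JNIR patients excluded from the PPS, of whom 2, 1 or 0 had TLF. Random removal would take 10 × 7/95 = 0.74 events on average.

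**Formula**
z = (pJ − pB − 0.05) / SE, with the SE evaluated at the maximum-likelihood rates constrained to differ by 0.05 (restricted MLE). The p-value is Φ(z). For 7/95 against 22/380, the difference is 0.0737 − 0.0579 = 0.0158 and the constrained rates are 0.1038 and 0.0538. Then SE = 0.0334, z = (0.0158 − 0.05)/0.0334 = −1.025 and p = 0.153.

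**Filter on JNIR only, BIONICS held at 22/380**

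| JNIR | Removed | Difference | p (restricted MLE) | At 0.10 |
|---|---|---|---|---|
| 7/95 (FAS) | none | 0.0158 | 0.153 | fail |
| 5/85 | 10, of whom 2 events | 0.0009 | 0.080 | pass |
| 6/85 | 10, of whom 1 event | 0.0127 | 0.144 | fail |
| 7/85 | 10, of whom 0 events | 0.0245 | 0.234 | fail |
| 6/94 | 1 event patient only | 0.0059 | 0.093 | pass |

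The statistic printed in SAP 15.1.2 uses the unpooled variance. With it, the one-sided 90% upper bound is 0.0534 for 7/95 (fail) and 0.0417 for 6/94 (pass). Removing a single early cardiac death from JNIR is enough to change the verdict in this example.

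**Chance of declaring non-inferiority when JNIR truly sits at the margin** (0.108 against 0.058, starting from 95 and 380, exact binomial enumeration). Here f is the share of event patients removed and g the share of event-free patients removed; both are assumed.

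| Filter | Apparent difference (points) | SAP statistic | Restricted MLE |
|---|---|---|---|
| None | 5.0 | 12.8% | 10.1% |
| JNIR only, f=20%, g=0 | 3.0 | 30.0% | 22.9% |
| Both groups, f=20%, g=0 | 4.1 | 20.2% | 14.4% |
| JNIR only, f=g=10% | 5.0 | 12.9% | 9.9% |
| JNIR only, f=0, g=10% | 6.1 | 8.6% | 5.7% |

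The filtered rate is p(1−f)/[p(1−f)+(1−p)(1−g)]. For JNIR with f=20%, g=0 it is 0.0864/0.9784 = 0.0883, and 0.0883 − 0.058 = 0.030. The same filter on BIONICS gives 0.0464/0.9884 = 0.0469, a difference of 0.041.

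Two things follow. The one-sided filter moves the result in whichever direction the exclusions fall. And a symmetric filter reduces the distortion without removing it, because it still selects on something that happens after baseline.

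**The case against.** The strongest reply is that the SAP never says BIONICS stays unfiltered. It uses set labels loosely: the FAS is defined as Japanese patients, yet "The clinical and angiographic covariates used in the propensity-score matching will be summarized for the FAS by treatment group", which stretches the label over both groups. The PPS label might be meant the same way, and the output templates are in a separate document. This stands as far as it goes. One-sided filtering is the natural literal reading, but the text does not state it. It does not rescue the plan, because no BIONICS criteria or re-matching rule exist for an analyst to follow.

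Three stronger readings are tempting, and the documents do not support them.
- That selected compliers would be compared with all-comers. The comparator is matched 4:1 on 13 covariates and comes from a trial with similar eligibility criteria (protocol 7).
- That the DAPT criterion cannot be applied to BIONICS. The exclusion is a duration, which is portable; only the regimen details in JNIR protocol 6.4.9.3 are specific to this trial. Whether BIONICS recorded DAPT in a usable form is not stated.
- That the bias probably favours JNIR. Early cardiac death pushes that way, but protocol 4.6 and 6.4.9.3 foresee stopping DAPT for severe bleeding, which can remove event-free patients and push the other way.

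The size of the example also depends on its inputs. With 10 removals the verdict changes only if 2 of them had events. If BIONICS lost events and non-events in the same proportions as the 5/85 case (about 16/340), the restricted-MLE p-value would be 0.126 (fail) and the printed SAP statistic would give 0.086 (pass).

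Finally, the verdict of the trial rests on the FAS, and no decision rule uses the PPS. That limits the consequence to the credibility of the robustness check.

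**Conclusion.** The point holds. The only sensitivity analysis of the primary endpoint uses a filter written in JNIR terms, including a post-baseline 12-month DAPT criterion, with no specified counterpart or re-matching for BIONICS. As written it is not like-for-like. A reader might infer a known bias towards JNIR; the documents support only that the bias may favour JNIR and can reverse if mainly event-free patients are removed. In the illustration the p-value runs from 0.080 to 0.234 against 0.153 in the FAS. That range rests on 7/95 events, 10 exclusions of whom 2, 1 or 0 had events, and BIONICS at 22/380; the documents give no exclusion or DAPT discontinuation rate. The SAP should be changed, but the primary FAS result does not depend on it.

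**What to change.** - **SAP 6.3 and 15.1.3:** define a BIONICS per-protocol pool by the same four criteria: valid consent, eligibility met, study stent received, and the same DAPT-duration rule judged under each trial's own regimen. Apply it before re-estimating the propensity score and redrawing the 4:1 matches, and say so. If BIONICS data cannot support a criterion, drop it from both sides.
- **Patients who die or have TLF before 12 months:** state one rule, identical in both groups, for how they are classed on the DAPT criterion, so that the endpoint itself does not cause exclusion. Symmetric filtering alone does not achieve this.
- **Reconcile two passages:** protocol 6.4.9.3 makes an exception to the 12-month requirement for medical necessity, while SAP 6.3 counts less than 12 months as a major violation without that exception.
- **Optional:** tabulate DAPT agent and persistence for JNIR and matched BIONICS, as a stated exception to SAP 17.

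The cost is SAP wording, one extra derivation and a slightly smaller matched PPS. Under SAP 5 one group already runs every analysis that uses both datasets.

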15.2. SECONDARY EFFICACY

The secondary efficacy analyses will be performed for the FAS.

15.2.1. SECONDARY EFFICACY VARIABLES & DERIVATIONS

15.2.1.1. Device, Lesion, and Procedure Success at Time of Baseline Procedure

 Device success is defined as achievement of a final in-stent residual diameter stenosis of <50% by Quantitative Coronary Angiography (QCA) in the target lesion, using the assigned device only and without a device malfunction. Device malfunctions are defined as occurring during the time of use.
 From final procedure QCA, Residual Diameter Stenosis (DS):

DS = 100*(1-mean (MIN1, MIN2) / mean (IS1, IS2)

Where 1 refers to projection = Projection 1

2 refers to projection = Projection 2

MIN: In stent minimum lumen diameter

IS: interpolated reference vessel diameter

If DS <50% and no device malfunction then Device Success = 1

Else if DS>=50% then Device Success = 0.

 Lesion success is defined as achievement of a final in-stent residual diameter stenosis of <50% (by QCA) in the target lesion using any percutaneous method.

From final procedure QCA, Residual Diameter Stenosis (DS) is calculated using the formula given above and:

If DS <50% then Lesion Success = 1

Else if DS \geq 50% then Lesion Success = 0.

Procedure success is defined as achievement of a final in-stent diameter stenosis of <50% (by QCA) using the assigned device and/or with any adjunctive devices, without the occurrence of cardiac death, Q wave or non-Q wave MI, or repeat revascularization of the target lesion during the hospital stay. Each Event is defined from adjudication, with peri-procedural MIs adjudicated per SCAI [2] definition.

The analysis of device success and lesion success will be performed on lesion level, i.e., the numerator will be the number of target lesions meeting the criteria for device or lesion success, respectively, and the denominator will be the total number of target lesions.

The analysis of procedure success will be performed on patient level, i.e., the numerator will be the number of patients with all target lesions meeting the criteria for procedure success and the denominator will be the total number of patients.

These analyses will be performed by Cardiovascular Research Foundation.

Document: T:\PROJ\Medinol\CXA27472\06 Biostatistics\Documentation\SAP\Final

1.0_08Aug2018\JNIR01_SAP_Final V1.0_08Aug2018.docx

Author: [name] Version Number: Final V1.0 Version Date: 08Aug2018

Template No: CS TP BS016 Revision 4 Reference: CS WI BS005

Effective Date: 01Apr2016

Copyright © 2009, 2010, 2012, 2016 Quintiles Transnational Corp. All rights reserved.

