6.4.7 Treatment Failures and Device Malfunctions of the MedJ-01

In case of failure to deliver a study stent, typical measures should be undertaken to ensure the lesion has been adequately prepared, such as use of appropriately sized pre-dilatation balloons, cutting or scoring balloons, and/or rotational atherectomy (including DCA) as appropriate. Guide

catheter support should be optimized using standardized techniques, including use of buddy wires and/or guide extension devices as appropriate. If the study stent can still not be delivered, any commercially available stent may be used to successfully and safely complete the procedure.

All failures and MedJ-01 malfunctions will be documented on the appropriate CRF. The MedJ-01 should be returned to Medinol for analysis and be reported in the clinical results. Instructions for returning the MedJ-01 are included in the trial's Site Binder. Treatment failures or device malfunctions should be reported in the CRF within 24 hours, per the instructions of EDC completion.

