6.4.8 Bail-out Stenting Procedures

Bailout stenting may be performed at the operator's discretion. If a bailout stent is required, a MedJ-01 stent of an appropriate diameter and length must be used. If a MedJ-01 stent of appropriate length and diameter is not available, an approved coronary stent should be used, preferably a second generation DES.

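### The coded device-success rule in SAP 15.2.1.1 leaves out the assigned-device-only condition, so a lesion finished with a non-study stent can count as a MedJ-01 success

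*SAP*

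**What the plan says.** SAP 15.2.1.1 first defines device success in words. Final in-stent DS must be below 50% by QCA, reached "using the assigned device only and without a device malfunction". Protocol 21.1 (Acute Success) gives the same three conditions.

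The SAP then turns this into a two-line rule. The first line is "If DS <50% and no device malfunction then Device Success = 1" and the second is "Else if DS>=50% then Device Success = 0". The analysis is per lesion, and "the denominator will be the total number of target lesions".

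Four other provisions bear on the rule:

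- Protocol 6.4.7: if the study stent still cannot be delivered, "any commercially available stent may be used to successfully and safely complete the procedure".
- Protocol 6.4.8: at bail-out, if no MedJ-01 of suitable size is available, "an approved coronary stent should be used, preferably a second generation DES".
- SAP 6.2: "Patients not receiving the study stent after it has been advanced beyond the guiding catheter will be analyzed in the FAS". Patients whose study stent was not implanted for a cause unconnected with the device are de-registered and leave the FAS.
- SAP 15.2: secondary efficacy is analysed on the FAS.

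**The concern.** Device success is meant to show whether the assigned stent, on its own and working properly, achieved the result. Lesion success asks only whether the result was achieved by whatever percutaneous means. The assigned-device condition is one of the two things that separate these endpoints, and the coded rule drops it. Whenever no malfunction is recorded, coded device success and coded lesion success are identical.

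A rescue with another manufacturer's stent could then be reported as a success of MedJ-01. The bias runs one way, in favour of the device. SAP 15.2.2 also reports this rate with an exact 95% confidence interval and a treatment-group difference, so an inflated value would carry into both.

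**Working it through.** The documents give no expected device-success rate for this trial, so there is no planned figure to reproduce. The check is one of logic, followed by an illustration of size.

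**1. Rule against definition.** There are eight combinations of three yes/no facts. The four with DS of 50% or more agree and are collapsed into the last row.

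| DS <50% | MedJ-01 only | Malfunction | SAP coded rule | Definition |
|---|---|---|---|---|
| yes | yes | no | 1 | 1 |
| yes | yes | yes | no value | 0 |
| yes | no | no | **1** | **0** |
| yes | no | yes | no value | 0 |
| no | either | either | 0 | 0 |

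The rule and the definition differ in 3 of the 8 combinations: one false success and two with no value.

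**2. Can the false success occur in the FAS?** Yes, by two routes.

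- *Non-delivery.* The stent passes the guiding catheter, cannot be delivered for a device-related reason, and the lesion is finished with a commercial stent (protocol 6.4.7). SAP 6.2 keeps the patient in the FAS. Whether this also counts as a malfunction is not settled. Protocol 14.7 lists non-delivery as a device deficiency, which SAP 17.2 makes the wider term. Protocol 6.4.7 names the two separately: "All failures and MedJ-01 malfunctions will be documented on the appropriate CRF".
- *Bail-out.* A MedJ-01 is already implanted, another stent is needed, and no suitable MedJ-01 is available (protocol 6.4.8). No malfunction is implied, and de-registration for non-implantation does not arise.

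**3. Size of the false-success error.** Let n be the number of target lesions and k the number with DS <50%, a non-study stent and no recorded malfunction.

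Overstatement = k/n

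Neither number is in the documents. I assume n = 100 to 150 (about 100 patients, some with more than one lesion) and k = 1 to 5.

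- Smallest: 1/150 = 0.7 points
- Middle: 3/120 = 2.5 points
- Largest: 5/100 = 5.0 points

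For the middle case with no other failures, exact (Clopper-Pearson) 95% intervals are:

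- by definition: 117/120 = 97.5% (92.9 to 99.5)
- by the coded rule: 120/120 = 100% (97.0 to 100)

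**4. The unset malfunction branch.** Take 2 lesions of 120 with DS <50% and a malfunction, and no other failures.

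- With the denominator in SAP 15.2.1.1 they are outside the numerator but inside the denominator: 118/120 = 98.3%, which matches the definition.
- If the general rule in SAP 7.1 were applied, which sets missing values aside, the result would be 118/118 = 100%.

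This gap therefore changes nothing as long as the endpoint-specific denominator is used.

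**The case against.** The best defence is that the SAP has not lost the condition. The correct definition stands in the same bullet, just above the coded lines. The numerator is described as lesions that meet the criteria, and a careful programmer would see all three. That is fair as far as it goes: this is a conflict inside one section. But the explicit 1/0 lines are the most specific text, and a programmer who follows them literally gets the wrong value.

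The route is also narrow. Non-implantation unconnected with the device leaves the FAS. Protocol 6.4.8 turns to another stent at bail-out only when no suitable MedJ-01 is to hand. Sites may record non-delivery as a malfunction. These points limit how often the error can occur. They do not make the rule right: a non-delivery recorded as a malfunction gets no value, not the 0 that the definition requires.

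The Clinical Events Committee adjudicates device non-success (protocol 8.4.1, SAP 4.1) and might catch such cases. The coded rule does not use that adjudication.

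The upper end of the size range is generous. In two earlier studies of the bare-metal platform, device success was 275/280 (protocol 3.3.1) and 350/354 (protocol 3.3.3). Non-success from all causes was therefore 5/280 = 1.8% and 4/354 = 1.1%. Applied to 100 to 150 lesions, that is about 1 to 3 lesions of every kind. These were different devices and can only illustrate, but they suggest that the lower half of the range is more plausible. This part of the objection stands.

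**Conclusion.** The concern holds. As coded, the rule gives 1 where the protocol and the SAP's own prose require 0, in a situation that the plan permits within the analysed population. The mismatch is certain from the text. Its effect depends on how many lesions are finished with a non-study stent without a recorded malfunction, which the documents do not give. Under the assumptions stated, the overstatement is 0.7 to 5.0 percentage points, and earlier experience with the platform points to the lower part of that range.

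The missing value for DS <50% with a malfunction is a secondary defect with no effect under the stated denominator. Patients de-registered for causes unconnected with the device are not affected. The endpoint is descriptive (SAP 7.5), and the primary TLF comparison is untouched. The rule should be corrected before programming, but it does not threaten the trial's main conclusion.

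**What to change.** Replace the two coded lines in SAP 15.2.1.1 with:

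- Device Success = 1 if DS <50%, only MedJ-01 stents were used in the target lesion, and no device malfunction occurred.
- Device Success = 0 for every other target lesion with known final DS, including DS <50% with a malfunction or with a non-study stent.

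Lesions with no final QCA are shown as missing and are not coded as failures by this rule. The denominator in SAP 15.2.1.1 stays as written and takes precedence over SAP 7.1.

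Add short statements on three matters: which data identify a non-study stent in a given lesion (procedure, treatment-failure and bail-out records), whether non-delivery counts as a malfunction for this endpoint, and how device non-success adjudicated by the committee enters the derivation.

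The cost is a few lines of text and no change to trial conduct. Treatment failures are already documented on the CRF (protocol 6.4.7), and bail-out is already summarised per patient (SAP 13). The documents do not show a stent-type field per lesion, so its availability must be confirmed. The reported rate may come out slightly lower.

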3.3.1 The PIONIR Study

This was the pivotal study conducted to demonstrate the safety and effectiveness of PresillionTM plus CoCr Coronary Stent on RX System (Presillion *plus* Stent System) in the treatment of *de novo* stenotic lesions in native coronary arteries. It was a post market study (for the EU, using an approved FDA protocol also supporting PMA submission) non-randomized, multi-center, prospective, single arm clinical study. Two hundred and seventy-eight (278) patients were enrolled to this study. Follow-up was performed at: discharge, 30 days, 180 days, 270 days, and 1 year.

The primary endpoint of the study was the incidence of target vessel failure (TVF) which was defined as the composite of cardiac death, target vessel myocardial infarction (Q-wave or

non Q-wave), or clinically-driven target vessel revascularization (TVR) by percutaneous or surgical methods, within 270 days of treatment with Presillion or Presillion *plus* Stent Systems.

Study results: The 270-day TVF rate was 8.9% and the upper bound of the exact one-sided 95% confidence interval was 12.3%. Since this upper bound is less than 16.46% (a performance goal derived using a meta-analysis of the standard-of-care therapy for coronary stenting with bare metal stents), the study stent is considered to have met the performance goal. Lesion success was achieved in 100.0% (280/280) of cases. Device success was achieved in 98.2% (275/280) of cases. Procedural success was achieved in 97.8% (272/278) of cases.

Conclusions: The 9-month results of the PIONIR study demonstrate Presillion Stent System and Presillion *Plus* Stent System to be safe and effective in the treatment of *de novo* stenotic lesions in native coronary arteries when compared to a performance goal derived using a meta-analysis of the standard-of-care therapy for coronary stenting with bare metal stents.[7]

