8.4 Other Aspects of Clinical Quality Assurance

8.4.1 Clinical Events Committee

The Clinical Events Committee (CEC) will be comprised of cardiologists who are not participants in the trial and who have no conflict of interest with the trial or the trial sponsor. All members of the CEC will be blinded to the primary results of the trial.

The CEC will be responsible for the adjudication of the clinical trial endpoint events. At the onset of the trial, the CEC will establish explicit rules outlining the process for adjudication and the algorithms followed in order to classify a clinical endpoint event. The CEC will also review and rule on all deaths that occur throughout the trial. In addition, the CEC will review and adjudicate device non-success. Definitions are provided in Section 21.1.

Once the specific criteria for clinical endpoints are established by the CEC, Cardiovascular Research Foundation will be responsible for preparing all clinical endpoint event dossiers and for the conduct of the CEC meetings.

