7. GENERAL CONSIDERATIONS

7.1. SUMMARY STATISTICS

Descriptive statistics of continuous variables will include number of observations available, mean, standard deviation, median, minimum, maximum, first quartile, and third quartile.

For categorical variables, the number within each category and the percentage out of the total number of observations available will be summarized. For that purpose, all variables with values missing, 'Unknown' or with values associated with 'Not applicable', 'Not Done', 'Not Reported' or 'Not Answered' will be set to missing and will not be included in the denominator for percentage calculation.

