8.3. MISSING DATA

Missing data will not be imputed (except for the purpose of reporting adverse events and medications by time point, see APPENDIX 2 for partial date imputation conventions).

All available data will be included in the safety analysis. Some efficacy analyses are based on excluding patients who do not have adequate follow-up time.

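### The SAP's device success rule gives no value to a lesion with residual stenosis below 50% and a device malfunction, and does not say how that lesion enters the rate

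*SAP*

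**What the plan says.** Protocol 21.1 and SAP 15.2.1.1 define device success by the same three conditions. Final DS must be below 50% by QCA, and in the SAP's words this must be reached "using the assigned device only and without a device malfunction. Device malfunctions are defined as occurring during the time of use".

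SAP 15.2.1.1 then turns the definition into a derivation with two branches: "If DS <50% and no device malfunction then Device Success = 1", followed by "Else if DS>=50% then Device Success = 0". There is no further branch.

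Three other rules bear on how a lesion without a value is handled:

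- SAP 15.2.1.1 puts lesions that meet the success criteria in the numerator, and "the denominator will be the total number of target lesions".
- SAP 7.1, a general rule for categorical summaries, says that missing and similar values "will be set to missing and will not be included in the denominator for percentage calculation".
- SAP 8.3 says "Missing data will not be imputed", with an exception only for reporting adverse events and medications by time point.

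Under SAP 15.2.2 and 15.2.2.1, device success is reported with an exact 95% confidence interval and compared between groups, with a 95% interval for the difference and a chi-square or Fisher p-value. SAP 7.5 and 8.4 make all secondary testing descriptive.

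**The concern.** By the definition, a malfunction is enough to make a lesion a device non-success, whatever the final angiogram shows. The derivation does not carry this through. A malfunction blocks the value 1 but cannot produce the value 0, because 0 depends on DS alone. A lesion whose stent malfunctioned but which was still opened to below 50% therefore gets no value.

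Protocol 14.7 lists foreseeable deficiencies such as stent expansion defect and balloon burst, and 6.4.7 tells the operator how to complete the procedure after a delivery failure. A malfunction with a good final result is therefore a case the rule has to cover.

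At stake is the device success rate and its comparison with BIONICS. SAP 15.2.1.1 assigns this analysis to an outside organisation working from the written specification, so the programmer has to choose between two denominator rules that give different answers.

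**Working it through.** **Step 1. Definition against derivation.** The table covers every combination of the three conditions.

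| Final DS | Malfunction | Assigned device only | Derivation | Definition |
|---|---|---|---|---|
| <50% | no | yes | 1 | 1 |
| <50% | no | no | 1 | 0 |
| <50% | yes | yes | no value | 0 |
| <50% | yes | no | no value | 0 |
| >=50% | either | either | 0 | 0 |

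The two malfunction rows with DS below 50% are the point at issue. The second row is a related gap: the first branch leaves out the assigned-device condition, so a lesion finished with another stent and without a malfunction is scored 1 against the definition.

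**Step 2. What a blank does to the rate.** Let N be the number of target lesions, k the number with DS below 50% and a malfunction, and f the number with DS of 50% or more. Assume that every other lesion is a success and has final QCA.

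- Denominator of SAP 15.2.1.1: rate = (N - k - f) / N
- Blanks dropped under SAP 7.1: rate = (N - k - f) / (N - k)

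The first formula gives the rate that the definition requires. The second is higher whenever k is above 0 and there is at least one success.

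**Step 3. Size.** The plan states no device success rate, lesion count or malfunction count, so there is no figure to reproduce and the inputs are assumptions.

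With f = 0:

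- N = 100, k = 5: 95/100 = 95.0% becomes 95/95 = 100%
- N = 120, k = 3: 117/120 = 97.5% becomes 117/117 = 100%
- N = 140, k = 1: 139/140 = 99.3% becomes 139/139 = 100%

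With N = 120 and f = 1:

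- k = 2: 117/120 = 97.5% becomes 117/118 = 99.2%
- k = 3: 116/120 = 96.7% becomes 116/117 = 99.1%
- k = 5: 114/120 = 95.0% becomes 114/115 = 99.1%

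**Step 4. The comparison with BIONICS.** If blanks are dropped in JNIR but malfunctions count as failures in BIONICS, the difference is biased in favour of JNIR. If blanks are dropped in both groups, both rates are inflated and the comparison no longer reflects any difference in malfunctions. The SAP does not say how the BIONICS flag is derived.

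**The case against.** The best reply is that SAP 15.2.1.1 already settles the rate. A malfunction lesion cannot enter the numerator, and the section's denominator keeps it in, so it counts as a non-success as the definition intends. A rule written for one endpoint is normally read as prevailing over a general one such as 7.1. Malfunctions are also tabulated separately under SAP 17.2, and the endpoint is descriptive.

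Much of this stands: on that reading the rate is right for malfunction lesions. It does not make the derivation complete, and the SAP nowhere says that 15.2.1.1 overrides 7.1.

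Three stronger readings are tempting, and the documents do not support them:

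- **Malfunctions disappear, and device success becomes the same as lesion success.** A malfunction lesion with DS below 50% is a lesion success but never a device success, so under the 15.2.1.1 denominator the two rates differ. They move together only if 7.1 is applied, and the separate tabulation remains in either case.
- **The PIONIR results prove the effect.** Protocol 3.3.1 reports lesion success in 280/280 and device success in 275/280, that is, "Device success was achieved in 98.2% (275/280) of cases". Dropping the five would give 275/275 = 100%. This requires PIONIR's definitions to match JNIR's and all five failures to be malfunctions, and the protocol states neither. The one reason it does give for device failure in an earlier study is a lesion that could not be reached because of tortuosity (3.3.6, two cases). A lesion like that, finished with another stent and with no malfunction recorded, would be coded 1 rather than left blank.
- **The derivation bypasses the clinical events committee.** Protocol 8.4.1 says "In addition, the CEC will review and adjudicate device non-success", and SAP 4.1 agrees. The derivation does not name the source of its malfunction input, so the text does not show that adjudication is ignored.

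**Conclusion.** The derivation is wrong as written. It fails to assign 0 to a lesion that the SAP's own definition makes a non-success. The effect on the result is conditional: none for malfunction lesions if the 15.2.1.1 denominator is used, and inflation if the blank is treated as missing under 7.1. In the second case, with the assumed counts, 95.0% to 99.3% becomes 100%, or 95.0% to 97.5% becomes 99.1% to 99.2% when one lesion in 120 has DS of 50% or more. The logical gap rests on the text alone, while the size rests entirely on the assumed counts. The primary TLF non-inferiority test is not touched. This is a drafting error to correct before the analysis is programmed, and it does not threaten the trial's main conclusion.

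**What to change.** Replace the two branches in SAP 15.2.1.1 with one exhaustive rule. For lesions with evaluable final QCA, Device Success = 1 if DS is below 50%, only the assigned device was used and there was no malfunction; otherwise Device Success = 0. This also closes the assigned-device gap.

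State that the 15.2.1.1 denominator overrides SAP 7.1 for this endpoint. Because lesions without final QCA then stay in the denominator without being successes, report how many there are. Apply the same rule to the matched BIONICS lesions.

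The prespecified denominator need not change, and committee-adjudicated non-success need not be added as a separate criterion, since the definition does not contain one. The cost is about one line of SAP text and code, and possibly a slightly lower reported success rate.
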